8.2 Variables

Medication

SAP 2-0:

Medication is recorded on a continuous medication log documenting free text for trade names. An allocation between trade names and medication categories will be continuously maintained and updated at least during the blind review prior to any data analysis.

Data file, identifier patient_ display_ id_full	Notes	Variable name		Variable level	Nominal values
medication_	no	cmbl	Baseline medication	nominal	∘ Yes ∘ No
log_details	report	cmtrt	Trade name	text	n.a.

Correction:

Medication is recorded on a continuous medication log documenting free text for trade names. An allocation between trade names and medication categories will be continuously maintained and updated at least during the blind review prior to any data analysis. For all patients for whom the medication date matches the date of the baseline, the baseline medication is set to yes.

Data file, identifier patient_ display_ id_full				Variable level	Nominal values
medication_	no	cmbl	Baseline medication	nominal	∘ Yes ∘ No
log_details	report	cmtrt	Trade name	text	n.a.
		cmstdt	Start date	date	n.a.

11 Analyses: Data of interest

SAP 2-0:

Correction:

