2.2 Data for which quality control is required

Although no endpoints are defined in this study, there will still be Quality Control for selected tables from the Baseline and Data of interest sections. The exact tables will be defined in a separate document.

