2.4 General information

This SAP may contain verbatim excerpts from the version of the CIP specified at the cover sheet. Such excerpts are *italicized with light blue background*.

The main aspects and the design of the clinical investigation are presented in chapters 2-3.

General statistical procedures are summarized in chapter 5. Those methods are used in case there is no other specification within this document.

Analysis set(s) and other global variables are defined in detail in chapter 6.

Descriptive and inferential statistical analyses for endpoint(s) are handled in following chapters. Thereby the following statistical considerations are specified:

- Analysis set: Definition of the analysis population (e.g. Intention-to-Treat or Per-Protocol for controlled clinical investigations or all patients with valid informed consent for singlearm clinical investigations)
- Variable characteristics: Description of all relevant variables (directly addressable from validated tools, e.g. CDMS or CDW, and derived variables) such as variable name, variable label, variable values, and data type.
- Derived variables, if applicable: For variables, which are not directly addressable from validated tools but are derived from other variables, pseudo-code or other instructions for the variable construction shall be provided.
- Missing, unused or spurious data: Specification of all data to be excluded from the specific analysis, e.g. data measured after a pre-specified point in time or implantation date after pre-hospital discharge date; specification whether and –if applicable– how to impute missing data.
- Data analysis: Description of descriptive, exploratory, and confirmatory analyses in text, tables, or pseudo-code shall be provided for unambiguous data analysis.

All variables are defined in tables using the following columns:

Data file: Name of a data file exported from the CDMS and CDW and unique identifier, if applicable (e.g. patient-specific "patient_display_ID_full" or event-specific record_ID); new data files ("data_SAR") may be generated by merging all relevant data from the original CDMS data files and generating derived variables;

Notes: Information whether data shall be presented with "descriptive" methods as defined in this SAP, data for "case listings" of original data for each patient specified, or "no report" for data needed for generating derived variables only;

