3.3 Design & time course

CIP chapter 8.1.1 Design type of clinical investigation

The study is designed as an explorative, open-label, prospective, non-randomized, multi-center, bi-national study.

CIP chapter 8.1.4 Methods

...

Data will be recorded at the following points in time:

- Enrollment / Baseline
- Implantation
- Pre-hospital discharge
- 1-month follow-up
- 3-month follow-up
- 12-month follow-up
- Termination

The following events can be documented at any time

- Adverse Event
- Device Deficiency
- Deviation (patient / site related)

4 Data source

All datasets are exported from the CDMS and CDW. All datasets from CDMS except adverse_event, device_deficiency, deviation forms and investigator_questionnaire are patient-specific, i.e. one data row per patient.

Scheduled Patient Forms

Dataset	Data rows,	Data rows	Parent CRF	Notes
name	unique identifier variables except record_id	unique identifier description	In case of embedded log	Notes
Enrollment	patient_display_id_full	Patient	n.a.	
Baseline - General	patient_display_id_full	Patient	n.a.	
Medical History	patient_display_id_full	Patient	n.a.	
Cardiac Diagnostics	patient_display_id_full	Patient	n.a.	
Device Log	patient_display_id_full & didvtyp	Patient & Device type	n.a.	 ○ Pacemaker SR-T ○ Pacemaker DR-T ○ CRT-P ○ RA lead ○ RV lead ○ LV lead ○ Other type of lead
Conc. Medication Log	n.a.		n.a.	
Implantation	patient_display_id_full		n.a.	
Lead Measurements	patient_display_id_full & prvisit		n.a.	Lead measurement optional at implantation, mandatory at PHD and 1-, 3- and 12-month follow-up. At 1-month FU HM data is acceptable
Pre-hospital Discharge	patient_display_id_full	Patient	n.a.	
Auto LVVO	patient_display_id_full	Patient	n.a.	
	patient_display_id_full		n.a.	
Follow-up - 1M	patient_display_id_full		n.a.	
Follow-up - 3M	patient_display_id_full		n.a.	
Follow-up - 12M	patient_display_id_full		n.a.	
Tachyarrhythmia Episodes	patient_display_id_full		Follow-up – 3M; Follow-up – 12M	
Study Termination	patient_display_id_full	Patient	n.a.	

Unscheduled Patient Forms

Dataset	Data rows,	Data rows	Parent CRF	Notes
		unique identifier	in case of	
	variables except	description	embedded	
	record_id		log	
Adverse Event	n.a.	Event	n.a.	
Hospitalization	n.a.	Event	Adverse	
Log			Event	
Device Deficiency	n.a.	Event	n.a.	
Deviation (patient	dvspid	Deviation ID	n.a.	
related)				

Site based forms

Dataset	Data rows,	Data rows	Parent CRF	Notes
name	unique identifier	unique identifier	in case of	

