6.3 Date of enrollment

CIP chapter 8 Design of the CliInical Investigation 8.3.4 Point of enrolment

The point of enrollment is defined as the time of signature of the informed consent form by the patient. Study related procedures, documentation and collection/following of adverse events will start from this time on.

Data file, identifier	Variable name			Nominal values
patient_ display_ id_full				
enrollment	dmicdt	3 \	date	n.a.
		Enrollment)		

7 Analyses: CONSORT diagram & "study realization"

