	descriptive if not blank	egpri	PR interval [ms]	scale	n.a.
	descriptive for	egqrs	, , , , ,	scale	n.a.
	cvegvrh = Intrinsic - atrial conducted OR Intrinsic - escape rhythm	egqrsm	QRS morpholgy	nominal	NormalLBBBRBBBIndeterminate

Cardiac diagnosis / left ventricular ejection fraction (LVEF)

Data file, identifier		Variable name		Variable level	Nominal values
patient_ display_ id_full					
cardiac_	descriptive	ehlvefas	LVEF assessed within 3 months prior to enrollment	nominal	∘ Yes ∘ No
diagnostics	Descriptive for	ehlvef	Left ventricular ejection fraction [%]	scale	n.a.
	ehlvefas = Yes				

Medication

Medication is recorded on a continuous medication log documenting free text for trade names. An allocation between trade names and medication categories will be continuously maintained and updated at least during the blind review prior to any data analysis.

identifier patient_	Notes			Variable level	Nominal values
display_ id_full					
medication_ log_details	no report	cmbl	Baseline medication	nominal	∘ Yes ∘ No
	no report	cmtrt	Trade name	text	n.a.

Data file, identifier patient_display_id_full			Variable label	Variable level	Nominal values
data_SAR	descriptive	aceinhib	BL med: ACE inhibitors	nominal	∘ Yes ∘ No
	for cmbl =	aldost_block	BL med: Aldosterone blocker	nominal	∘ Yes ∘ No
	Yes	angiotens_rec_block	BL med: Angiotensin receptor blocker	nominal	∘ Yes ∘ No
		antiarrhythmics	BL med: Antiarrhythmics	nominal	∘ Yes ∘ No
		anticoagulation	BL med: Anticoagulation	nominal	∘ Yes ∘ No
		antiplatelets	BL med: Antiplatelets	nominal	∘ Yes ∘ No
			BL med: Betablocker (excluding sotalol)	nominal	∘ Yes ∘ No
		ccblocker	BL med: Calcium channel blocker	nominal	∘ Yes ∘ No
		digitalis	BL med: Digitalis	nominal	∘ Yes ∘ No
		diuretics	BL med: Diuretics (other than	nominal	∘ Yes ∘ No
			Aldosterone blocker)		
		statins	BL med: Statins	nominal	∘ Yes ∘ No
		other_cv_med	BL med: Other cardiovascular medication	nominal	∘ Yes ∘ No
		non_cv_med	BL med: Non-cardiovascular medication	nominal	∘ Yes ∘ No

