11.1 Baseline characteristics and medical history

See chapter 8.

11.2IPG-related SADE-free rate (see definition below)

CIP chapter 8 Design of the CliInical Investigation 8.1. General considerations

...

Definition of SADEs to be taken into account for the calculation of the SADE-free rate: SADEs will be adjudicated internally, whereby the seriousness and device relatedness will be reexamined.

If any amply documented external physical influence (e.g. accident, sport, twiddling) or other causative AE led to the SADE, the SADE does not contribute to the calculation of the SADE-free rate. Only SADEs directly related to the investigational device (SADE-d) will be included in the analysis. SADEs which are securely related to the implantation procedure (SADEp) (e.g. pocket infection, etc.) will not be considered for the analysis. Furthermore Twiddler's syndrome will not be considered for the analysis either.

...

CIP chapter 12 Statistical Design and Analysis 12.2. Descriptive statistics

. . .

The SADE-free rate is calculated using the Kaplan-Meier estimate after 12 months.

Data file, identifier record_id				Variable level	Nominal values
internal_ adjudication	no report	aestdt	Onset date	date	n.a.
adjudication			Adverse Event is relevant for SADE-free rate	nominal	∘ Yes ∘ No

Data file, identifier patient_ display_ id_full	Notes	Variable name		Variable level	Nominal values
data_SAR	no report	date_implantation_SAR	Date of implantation	date	n.a.
		date_terminaton_SAR	Date of study termination	date	n.a.
		date_1stsade_SAR	Date of first SADE	date	n.a.
		date_censoring_SAR	Date of censoring (date_1stsade_SAR OR date_terminaton_SAR)	date	n.a.
	descriptive and 95% CI,	any_sade_SAR	Any Serious Adverse Device Effect based on internal adjudication	nominal	YesNo
	Kaplan Meier analysis	days_impl_censoring_SAR	Days from implantation to censoring	date	n.a.

Data file, identifier patient_ display_ id_full	Notes	Variable name	Variable label	Variable Level	Nominal values
internal_	case listing	aestdt	Onset date	date	n.a.
adjudication		primdt	Date of implantation	date	n.a.
		aerelidv	Adverse Event is related to the investigational device (device related ADE)	nominal	○ Not related○ Unlikely○ Possible○ Probable○ Causal relationship
		corelidv	Please specify	text	n.a.
		aeser	Adverse Event is serious	nominal	∘ Yes ∘ No
		aerelset	Adverse Event is relevant for SADE-free rate	nominal	∘ Yes ∘ No
		corelset	Please specify reason for "No"		∘Yes ∘No

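### Does the erratum's baseline-medication rule count drugs started after baseline as baseline drugs?

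*SAP*

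**What the plan says.** SAP 2.0, section 8.2 (Medication), describes the source: "Medication is recorded on a continuous medication log documenting free text for trade names". The file medication_log_details holds the Yes/No flag cmbl and the trade name cmtrt. Thirteen drug-class variables, from ACE inhibitors to non-cardiovascular medication, are then described for entries with cmbl = Yes. SAP 2.0 gives no derivation for cmbl; it is used as collected.

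The erratum keeps this text, adds the start date cmstdt to the same file, and adds one sentence: "For all patients for whom the medication date matches the date of the baseline, the baseline medication is set to yes".

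SAP chapter 4 (Data source) bears on the number of rows per patient. Its opening text says: "All datasets from CDMS except adverse_event, device_deficiency, deviation forms and investigator_questionnaire are patient-specific, i.e. one data row per patient". The medication log is not among those exceptions. In the table that follows, the line for the "Conc. Medication Log" shows n.a. in the identifier column.

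No variable is named for the baseline date. Section 6.3 defines only the enrollment date, dmicdt: "The point of enrollment is defined as the time of signature of the informed consent form by the patient".

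**The concern.** The erratum's condition picks out patients, but the thing being set belongs to a single drug entry. A continuous log that feeds 13 drug classes will hold several entries for many patients. If a patient qualifies through one entry dated at baseline, the sentence could be taken to set all of that patient's entries to Yes. A drug first given at month 3 would then appear in the baseline table, and the frequencies of some drug classes would be too high.

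The SAP sets itself a standard that this sentence does not quite meet. Section 2.4 says that the description of each analysis "shall be provided for unambiguous data analysis". Section 2.2 adds that "there will still be Quality Control for selected tables from the Baseline and Data of interest sections". If the medication table were among those selected, two people following the text might produce different tables. Chapter 8 is also the first item of the data of interest, section 11.1, "Baseline characteristics and medical history".

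**Working it through.** The plan states no figure to reproduce, so the check has two parts: what the sentence does under each reading, and which reading the documents support.

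**Three readings.** For log entry *i* of a patient:

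- Per entry, recorded flag kept: Yes if cmstdt(*i*) equals the baseline date; otherwise the recorded cmbl(*i*).
- Per patient: Yes if any entry of that patient has cmstdt equal to the baseline date; otherwise the recorded cmbl(*i*).
- Per entry, recorded flag replaced: Yes only if cmstdt(*i*) equals the baseline date; otherwise No.

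The log below is invented for illustration. Start is in days from baseline.

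| Patient | Drug | Start | Recorded cmbl | Per entry, kept | Per patient | Per entry, replaced |
|---|---|---|---|---|---|---|
| 1 | ACE inhibitor | 0 | No | Yes | Yes | Yes |
| 1 | statin | -400 | Yes | Yes | Yes | No |
| 1 | anticoagulant | 120 | No | No | Yes | No |
| 2 | beta-blocker | -30 | Yes | Yes | Yes | No |
| 2 | antiarrhythmic | 60 | No | No | No | No |
| 3 | diuretic | 0 | No | Yes | Yes | Yes |
| **Total Yes** | | | 2 | 4 | 5 | 2 |
| **Yes, started after baseline** | | | 0 | 0 | 1 | 0 |
| **No, recorded Yes before baseline** | | | 0 | 0 | 0 | 2 |

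The feared error appears only in the per-patient column, and only for a patient who also has an entry dated at baseline.

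**Which reading the text supports.**

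1. The test is a match of dates. The erratum brings in cmstdt for this purpose and lists it beside cmbl and cmtrt in one file. The drug started on day 120 fails the test. To flag it, the reader must add that a match on one entry carries over to the patient's others, and the sentence does not say so.
2. The sentence only sets Yes. It never sets No, so replacing the recorded flag also needs an unstated step. Recorded Yes values for drugs begun before baseline therefore stand.
3. The n.a. in chapter 4 does not mean that the log lacks a row key. That column lists identifiers other than record_id. Adverse Event, Hospitalization Log and Device Deficiency carry the same n.a., and the table describes each of them as one row per event. The medication log fits that pattern of one row per record.
4. The one-row-per-patient sentence in chapter 4 is not reliable on this point. The table beneath it keys the Device Log by patient and device type, and Lead Measurements by patient and visit, and neither is a named exception. One trade name per patient could not feed 13 drug classes either.

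**Size.** Under the per-entry reading the over-count is 0. Under the per-patient reading, assuming independence, it would be *q* × *r* for each drug class. Here *q* is the share of patients with an entry dated at baseline, and *r* is the share who start that class only after baseline. The documents give neither, so any number would be an assumption. For scale, one patient of the planned 50 (CIP Amendment 2) is 100 / 50 = 2 percentage points in one line of the table.

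**The case for a change.** The strongest argument for a change is that this sentence is the only rule in the documents for setting cmbl, that its stated unit is the patient, and that one better sentence would remove any doubt. It also leaves three details unsaid: which variable holds the baseline date, whether recorded values are kept, and what happens to an unflagged drug begun before baseline and still taken. The SAP's convention of marking derived variables with SAR is not followed either, so recorded and altered values share the name cmbl.

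All of this stands as comment on the wording. None of it shows a wrong table. SAP 3.3 lists enrollment and baseline as a single time point, so an analyst choosing between the consent date and a date on the baseline form has a narrow choice. Unflagged drugs begun earlier are not reached by the per-entry rule, but nothing in the documents shows that any exist, and the recorded flag is there to capture them. The per-patient reading would also not be wrong in every extra entry: an earlier drug still taken at baseline would be flagged correctly.

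The quality-control argument cannot be taken further. Section 2.2 leaves the list of tables to a separate document, so it is unknown whether this table is included.

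**Conclusion.** No change to the plan is called for. The unit in the erratum's sentence is a clerical slip, and the missing details are a gap that an analyst fills sensibly by comparing each entry's start date with the baseline date and leaving recorded Yes values alone. Done that way, no drug started after baseline enters the baseline table.

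This rests on two inferences. The first is that the log has one row per record, which chapter 4 indicates but does not state outright. The second is that the match was run entry by entry, which the placement of cmstdt beside cmbl makes the natural course.

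If the second inference were wrong, the damage would be confined to a descriptive table of 13 drug classes. The study has no hypotheses or endpoints, and neither the SADE-free rate nor any performance measure uses cmbl.

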11.2 IPG-related SADE-free rate (see definition below)

SAP 2-0:

Data file, identifier patient_ display_ id_full	Notes	Variable name	Variable label	Variable Level	Nominal values
internal_	case listing	aestdt	Onset date	date	n.a.
adjudication		primdt	Date of implantation	date	n.a.
		aerelidv	Adverse Event is related to the investigational device (device related ADE)	nominal	 ○ Not related ○ Unlikely ○ Possible ○ Probable ○ Causal relationship
		corelidv	Please specify	text	n.a.
		aeser	Adverse Event is serious	nominal	∘Yes ∘No
		aerelset	Adverse Event is relevant for SADE-free	nominal	∘ Yes
			rate		o No
		corelset	Please specify reason for "No"		∘ Yes
]				o No

Corrections:

If no SADEs occurred during the observation period, the binomial confidence interval is calculated in addition to the Kaplan-Meier estimator. Taking into account all patients of the analysis set and in addition only a subgroup of patients with documented 12-month follow-up.

Data file, identifier patient_ display_ id_full	Notes		Variable label	Variable Level	Nominal values
	case listing if relevant	aestdt	Onset date	date	n.a.
adjudication	for SADE-free rate	primdt	Date of implantation	date	n.a.
	descriptive if evaluated	aeser	Adverse Event is serious	nominal	∘ Yes
					⊙ No
		aerelidv	Adverse Event is related to	nominal	○ Not related
			the investigational device		o Unlikely
			(device related ADE)		o Possible
					o Probable
					○ Causal relationship
		aerelset	Adverse Event is relevant for	nominal	∘Yes
			SADE-free rate		∘ No
	descriptive for aerelset	corelidv	Please specify	text	o n.a.
	= No	corelset	Please specify reason for "No"	text	o n.a.

11.3 Lead measurements (sensing amplitude, pacing threshold, pacing impedance at implantation and at each follow-up and/or via Home Monitoring)

Coronary Sinus (CS) Lead Measurements - Left ventricle (LV)

SAP 2-0:

Data file,	Notes	Variable	Variable	Variable	Nominal
identifier		name	label	level	values
patient_					
display_					
id_full					
lead_	descriptive	dulvsv	Permanently programmed	nominal	oLV1 tip to LV2 ring (bipolar)
measurements	by prvisit		LV sensing vector		oLV1 tip to Can (unipolar)

Correction:

Data file, identifier patient_ display_ id_full	Notes		Nominal values
measurements		Permanently programmed LV sensing vector	oLV1 tip to LV2 ring (bipolar) oLV1 tip to Can (unipolar)

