12.1 Analysis population

All patients with valid patient informed consent are included in the analysis set.

CIP chapter 9.3 Implantation

If the implantation is not performed within 30 days of the informed consent, the patient may be excluded from the study

- 4.44				Nominal
patient_display_id_full	name	label	level	values
enrollment	dmsubsps	Patient signed the informed consent personally	nominal	∘ Yes
				∘No
enrollment	dmrprsps	An independent witness signed the informed	nominal	∘Yes
		consent since the patient is unable to write		o No
data_SAR	analysis_set_	Enrollment analysis set	nominal	∘ Yes
	enr_SAR			∘No

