7.1.4 Patients excluded from the analysis set

Patients without valid patient informed consent are excluded from the analysis. Other reasons:

CIP chapter 9.3 Implantation

If the implantation is not performed within 30 days of the informed consent, the patient may be excluded from the study

Inclusion criteria

Data file,	Notes	Variable	Variable	Variable	Nominal
identifier		name	label	level	values
patient_					
display_id_full					
enrollment	descri	tiinc01	Standard indication for pacemaker or cardiac	nominal	Yes
	ptive		resynchronization therapy pacemaker (CRT-P)		∘ No
			implantation, including de novo, upgrade or replacement		
			implantations		
		tiinc02	Ability to understand the nature of the study	nominal	Yes
					∘ No
		tiinc03	Willingness to provide written informed consent	nominal	Yes
					∘ No
		tiinc04	Ability and willingness to perform all follow-up visits at	nominal	o Yes
			the study site		∘ No
		tiinc05	Ability and willingness to use the CardioMessenger and	nominal	o Yes
			acceptance of the BIOTRONIK Home Monitoring concept		∘ No

Exclusion criteria

Exclasion criteria					
Data file,	Notes	Variable	Variable	Variable	Nominal
identifier		name	label	level	values
patient_display					
_id_full					
enrollment	descri	tiexc01	Planned for conduction system pacing	nominal	o Yes
	ptive				∘ No
		tiexc02	Planned for activation of aATP without known history of	nominal	o Yes
			atrial arrhythmia, or with permanent AF		o No
		tiexc03	Planned cardiac surgical procedures or interventional	nominal	o Yes
			measures other than the study procedure within the		∘ No
			next 12 months		
		tiexc04	Pregnant or breast feeding	nominal	o Yes
					o No
		tiexc05	Age less than 18 years	nominal	o Yes
					o No
		tiexc06	Participation in another interventional clinical	nominal	o Yes
			investigation		∘ No
		tiexc07	Life-expectancy less than 12 months	nominal	o Yes
					∘ No

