7.2 Termination

- 7.2.1 Date of first-patient-out (FPO)
- 7.2.2 Date of last-patient-out (LPO)
- 7.2.3 Premature study termination / drop-out

Data file: Identifier patient_ display_id_ full	Notes	Variable name	Variable label	Variable level	Nominal values
study_ termination	descriptive	dsrtrm	Regular study termination	nominal	o Yes o No
termination		dsetrrea	Reason for early study termination		 Patient unable to attend required visits Patient is lost to follow-up Patient withdrew consent to study participation Patient death Drop-out according to protocol Enrollment failure

Data file: Identifier patient_displa y_id_full		Variable name	Variable label	Variable level	Nominal values
enrollment	Case listing for dsetrrea = Drop-out	dmicdt_i	Patient: Date of informed consent signature	date	n.a.
/ —	according to protocol	dstrdt_i	Date of study termination	date	n.a.
		dsdrppro	Please specify "Drop-out according to protocol"	nominal	o No implantation attempted within 30 days of enrollment ○ Not implanted with an investigational device ○ Investigational device was explanted and will not be replaced with corresponding BIOTRONIK device ○ Other
		CODRPPRO	Please specify "Drop-out according to protocol - Other"	text	n.a.

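### With zero SADEs, the first binomial interval in SAP erratum 11.2 uses the consent-based set, so a patient never exposed to the device and left in that set counts as SADE-free

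*SAP*

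**What the plan says.** - **Trigger and denominators (SAP erratum 11.2).** "If no SADEs occurred during the observation period, the binomial confidence interval is calculated in addition to the Kaplan-Meier estimator". Two groups are named for that interval: "Taking into account all patients of the analysis set and in addition only a subgroup of patients with documented 12-month follow-up".
- **Analysis set (SAP 6.1, citing CIP 12.1).** "All patients with valid patient informed consent are included in the analysis set". The flag analysis_set_enr_SAR is tabulated with consent variables only. No implanted or safety set is visible.
- **Enrolment (SAP 6.3).** "The point of enrollment is defined as the time of signature of the informed consent form by the patient".
- **Exclusion route (SAP 6.1 and 7.1.4).** "If the implantation is not performed within 30 days of the informed consent, the patient may be excluded from the study".
- **Drop-out reasons (SAP 7.2.3).** The termination form provides for "No implantation attempted within 30 days of enrollment" and "Not implanted with an investigational device".
- **Events counted (definition in SAP 11.2).** "Only SADEs directly related to the investigational device (SADE-d) will be included in the analysis".
- **Time scale (SAP 11.2).** The Kaplan-Meier time variable counts days from implantation. The same table orders a percentage and 95% CI for any_sade_SAR.

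**The concern.** A patient who never came into contact with an investigational device cannot have a serious event directly related to it. If such a patient stays in the consent-based set, the first binomial interval treats that patient as evidence of device safety. In the Kaplan-Meier analysis a patient without an implantation date has no time at risk, so two estimates of the same rate, printed together, could describe different groups.

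The SADE-free rate bears on the primary objective in SAP 3.1: preliminary safety, and data for the market-release decision. With zero events the Kaplan-Meier estimate is 100% and its Greenwood variance is zero, so the binomial lower bounds carry all the expressed uncertainty. Unexposed patients in the denominator can move the first bound in one direction only, in favour of the device.

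**Working it through.** The documents give no rate, interval or sample-size calculation for the SADE-free rate (SAP section 5, item 12.5, says none is needed), so there is no planned figure to reproduce. The check has two parts.

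**1. Who is in each denominator, on the visible text**

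| Patient | Consent-based set (first interval) | 12-month follow-up subgroup (second interval) | Kaplan-Meier from implantation |
|---|---|---|---|
| Implanted with study device, followed to 12 months | in | in | in |
| Implanted with study device, left or died before 12 months | in | out | in, censored |
| Study device attempted, not left in place | in | probably out | unclear |
| Non-study device only | in, unless removed | probably out | unclear |
| No implantation attempted | in, unless removed under the 30-day rule | out in practice | no time at risk |

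The two unclear cells arise because erratum 11.5 labels date_implantation_SAR as a procedure date. An attempted implant, or a non-study device, could therefore carry a date.

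The first interval can thus include unexposed patients, while the second leaves out exposed patients who ended early. Such patients exist: erratum 11.15 refers to patients who died before the 12-month visit. Neither interval is defined on the exposed patients.

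**2. Size of the effect**

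Inputs: 50 patients planned (CIP amendment 2, entries for the synopsis and section 8.2.3); zero events (the erratum's own condition); 95% level (SAP 11.2), taken as two-sided; binomial interval (SAP section 5, item 12.3), taken as exact Clopper-Pearson. The number k of unexposed patients among the 50 is an assumption, because the documents give none.

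With n of n patients event-free, the lower bound L solves L^n = 0.025, so L = 0.025^(1/n).

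For n = 50: ln(0.025) = −3.6889; divided by 50 this is −0.07378; exp(−0.07378) = 0.92888.

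| k (assumed) | n = 50 − k | Lower bound | Points below n = 50 |
|---|---|---|---|
| 0 | 50 | 92.89% | 0 |
| 1 | 49 | 92.75% | 0.14 |
| 2 | 48 | 92.60% | 0.29 |
| 3 | 47 | 92.45% | 0.44 |
| 4 | 46 | 92.29% | 0.59 |
| 5 | 45 | 92.13% | 0.76 |
| 10 | 40 | 91.19% | 1.70 |

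The exact bounds agree with the beta quantile. Wilson bounds, computed for every row except k = 4, lie within 0.05 points of them. The point estimate stays at 100% throughout. For k up to 5 the shift is about 0.15 points per patient (0.76 / 5 = 0.15).

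**The case against.** **Text may be missing.** SAP 2.4 says each analysis names its analysis set, and chapter 8 does so. The opening of chapter 11 is not visible, and the erratum's own entry for chapter 11 is blank in the available text. A statement there could already fix the denominator. This stands as a limit on the finding, which can be made only on the visible text.

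**The 30-day rule removes these patients.** A reader might infer that every enrolled patient who was never implanted counts as SADE-free. The documents do not support that. The rule is attached to the analysis-set definition and repeated in the section on exclusions from the analysis set, so some such patients may leave. But it is permissive, it does not settle whether leaving the study means leaving the analysis set, and it does not clearly cover a patient given a non-study device within 30 days. It narrows the problem without closing it.

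**The plan follows the CIP.** CIP 12.1 includes all consented patients, and CIP 12.12 places the safety analysis in the total study population. The first point stands, so a restriction must be declared. The second contrasts safety with subgroup analyses by device type and sex. It does not address unexposed patients in a device-related rate.

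**Safeguards exist.** The 12-month interval would in practice leave out most never-implanted patients, SAP 7.2.3 lists protocol drop-outs with reasons, and section 5, item 12.13, requires missing counts and drop-outs to be reported. A reader could probably work out how many patients are affected. None of this gives an interval on the exposed patients.

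**Nothing turns on it.** There are no hypotheses, endpoints or pass/fail criteria, and all analyses are exploratory. That is correct, and it sets the priority.

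**Conclusion.** On the visible text the point holds in a limited form. The first zero-SADE interval is defined on a consent-based set, so an unexposed patient who remains in that set raises the lower bound of a device-related rate. The set is also not aligned with the implantation-based Kaplan-Meier analysis printed beside it.

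The size is about 0.15 points per such patient around a bound of 92.9%: 0.29 points for two patients and 0.76 for five. This rests on 50 enrolled patients, zero events, an exact two-sided 95% interval and an assumed number of unexposed patients. That number may be zero, in which case nothing changes. It also rests on there being no chapter 11 analysis-set statement in the text that cannot be seen.

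A reader might go further and infer that the reported safety rate is materially inflated. The documents do not support this: no unexposed patient is documented, the point estimate is unaffected, and there is no threshold for the bound to cross. The priority is minor; the reason to act is a correct and stated denominator.

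**What to change.** In erratum 11.2, define the first binomial group as *patients of the analysis set in whom an investigational device was implanted or its implantation attempted*. Use the same group for the any_sade_SAR percentage and 95% CI in 11.2. Attempted implantations belong in it because those patients had contact with the device; the device status list in SAP 11.5 provides for them.

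Report how many enrolled patients fall outside this group. Print the denominator of each binomial interval and of the Kaplan-Meier estimate. Do not assume that the new group equals the Kaplan-Meier population: if the numbers differ, say why. Keep the interval in patients with documented 12-month follow-up. If a chapter 11 analysis-set statement already settles the denominator, a cross-reference in 11.2 is enough.

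The cost is one phrase, the printed denominators and a re-run of one table. The report should note that the CIP 12.1 set is restricted for this one rate; it stays in use elsewhere. The downside is a slightly less favourable lower bound, or none if every enrolled patient was exposed.
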